The use of intravesical gentamicin sulfate as a clinical strategy to prevent UTIs has been shown to be successful and safe in treating and suppressing recurrent UTIs in both adults and children (41-43). The administration of aminoglycosides (having primarily bactericidal activity against Gram-negative aerobes and facultative anaerobic bacilli) intravesically permits the use of high concentrations of antimicrobial solution targeting a local pharmacological effect while limiting systemic adverse effects such as nephrotoxicity, or impacting gastrointestinal flora. This approach helps prevent the development

of antimicrobial resistance. From the various aminoglycosides, gentamicin remains the best studied of these agents for bladder washout use and is the only intravesical treatment that has been shown to be safe and effective in both the prevention and treatment of UTIs (44, 45).

II. General Experimental Design

A. Objectives: The purpose of this feasibility study is to address the prevalence of chronic, recurrent urinary tract infections in adults living with a chronic, severe, spinal cord injury (SCI). We propose to determine if daily gentamicin bladder instillations reduce the rate of symptomatic UTIs as well as the use of oral and intravenous antibiotics in adults with chronic SCI who have recurrent UTIs. This study will test the efficacy of intravesical gentamicin delivery and provide insights into the mechanisms that underlie the benefits of this local pharmacological effect for translation into the clinic.

Overall Hypothesis: The use of a daily gentamicin instillation treatment will significantly decrease the incidence of catheter-associated complications, such as chronic symptomatic urinary tract infections as well as improve urological outcomes, thus greatly enhancing the quality of life for individuals with bladder dysfunction.

Specific Aim 1: To assess the effects of gentamicin bladder instillation (saline instillation and no instillation will serve as controls) on:1) bacteriuria (number and species, antimicrobial resistant bacteria, urinary leukocytes, and urinary pH), 2) risk factors for developing UTI (over-distention of the bladder, high-pressure voiding, large post-void residuals, detrusor sphincter dyssynergia, presence of stones, and signs of hydronephrosis resulting from vesico-ureteral reflux), and 3) individual tolerability (blood pressure outcomes).

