Hypothesis 1.1: Bladder instillation with a gentamicin antimicrobial solution will result in significantly decreased episodes of symptomatic UTIs, fewer courses of oral antibiotics, and a reduction of multi-drug resistant organisms on urine culture, as compared to controls.

Hypothesis 1.2: Bladder instillation with a gentamicin antimicrobial solution will decrease detrusor spasms, increase bladder compliance as well as mitigate the rapid rise in systolic blood pressure (autonomic dysreflexia) evidenced during cystometry as compared to controls.

B. Study Design/Methodology

In a randomized, double-blind, prospective study, we will compare the long-term effects (80 daily sessions, 2x per day) of a bladder instillation protocol in 3 groups of individuals (n=36; 3 groups of 12) with chronic SCI receiving either:

1) gentamicin bladder instillation

2) saline installation

3) no instillation (catheter clamping only in those with suprapubic catheters for the duration of the irrigation time frame - refer to Fig. 2 timeline).

The control groups will also serve to address the question of whether bacteria already colonized in the bladder would also provide a protective role in preventing more pathogenic bacteria or other organisms, such as yeast, which also colonize the bladder. Research participants will complete the 80 sessions of twice per day instillations initially in the Urogenital and Bowel Laboratory, where blood pressure and heart rate will be continually monitored (approximately 1-2 weeks). Once safe pressures are established, the remaining instillations may be completed in the home setting. A major issue confounding validity of a clinical trial is compliance. Given that this study assesses the long-term outcomes of daily bladder instillations and allows for the twice-daily instillations to be conducted in the home-setting, it is possible that participants may not be fully

compliant with respect to study duration and frequency of instillations. In an effort to improve the applicability of the study results to individual participants and mitigate non-compliance, our research nurse will guide participants through all aspects of the instillation procedure to ensure that they are fully independent. At-home blood pressure monitoring during instillation times is automatically recorded and will be an additional step in monitoring protocol adherence.

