We propose to use a sample size of 36 (12 in each of the three arms). Cox et al., (46) has found that the use of intravesical gentamicin was associated with a reduction of a median 3 symptomatic UTIs in 6 months in 22 patients. Using the formulas proposed by Hozo et al., (47) we estimated the corresponding standard mean change to be 2.48 with a standard deviation of 1.7. Assuming the same standard deviation in our data, a sample size of 12 achieves 80% power to detect a mean of paired differences of as low as 1.5 symptomatic UTIs for the gentamicin group with a significance level of 0.05 using a two-sided paired ttest (48, 49). We expect to observe a drop of at least 2 symptomatic UTIs in 6 months. With the same setting, i.e. SD = 1.7, a sample size of 12 achieves 97% power to detect that. Our study will compare changes between the gentamicin instillation, the saline instillation and the no-instillation groups. We will use the comparison between the gentamicin and the non-instillation group to estimate the power. The estimated effect of gentamicin is a reduction in symptomatic UTIs of 2 with a standard deviation of 1.7 (described above) and we assume no change for the non-instillation group (mean reduction of 0 with a standard deviation of 0). With these values, sample sizes of 12 (gentamicin) and 12 (no-instillation) achieve 96% power to reject the null hypothesis of equal means with a significance level of 0.050 using a two-sided two-sample unequal-variance t-test (48-51). The power analysis was performed in PASS 14 Power Analysis and Sample Size Software (NCSS, LLC. Kaysville, Utah, USA, ncss.com/software/pass).

Experimental Outcomes – Research Procedures

1. Intravesical Gentamicin Sulfate Instillation

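### Six hypothesised efficacy outcomes share the same tests with no designated primary outcome, order or adjustment, so the chance of a false finding is not held at the level for one outcome

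*Combined protocol and SAP*

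**What the plan says.** All references are to the combined protocol and SAP.

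- **II.A, Objectives.** The study is introduced with "The purpose of this feasibility study", yet the same paragraph states "This study will test the efficacy of intravesical gentamicin delivery". The stated aim joins two outcomes: to "reduce the rate of symptomatic UTIs as well as the use of oral and intravenous antibiotics".
- **II.A, Hypothesis 1.1** names three outcomes: "significantly decreased episodes of symptomatic UTIs, fewer courses of oral antibiotics, and a reduction of multi-drug resistant organisms on urine culture".
- **II.A, Hypothesis 1.2** names three more: gentamicin instillation "will decrease detrusor spasms, increase bladder compliance as well as mitigate the rapid rise in systolic blood pressure" during cystometry. Both hypotheses are framed against the control groups.
- **II.A, Specific Aim 1** lists further measures, beginning with "bacteriuria (number and species, antimicrobial resistant bacteria, urinary leukocytes, and urinary pH" and going on to UTI risk factors and blood pressure. Six is therefore a minimum.
- **II.B.2, Statistical Plan** prescribes a paired t-test of change in each group and a three-group ANOVA of the changes. Pairwise two-sample t-tests follow if the ANOVA is significant, and non-parametric equivalents are used if assumptions fail. No outcome is singled out, and no order or adjustment across outcomes is given.
- **II.B.2, power paragraph** concerns symptomatic UTIs only, at two-sided 0.05. On the between-group calculation it says "We will use the comparison between the gentamicin and the non-instillation group to estimate the power".

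**The concern.** The ANOVA gate limits the number of pairwise comparisons within one outcome. It does nothing across outcomes, and the paired tests are not gated at all. With six hypothesised outcomes treated alike, the overall chance of a false significant result is higher than for any one of them. Nothing in the plan stops a different outcome from leading the report if symptomatic UTI shows no effect.

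The feasibility label does not settle this. The plan says that it tests efficacy, predicts a significant decrease and gives formal power for an efficacy comparison. At stake is whether a reported benefit of gentamicin can be read at its nominal error rate.

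**Working it through.** **1. The plan's own power figures.** Inputs from II.B.2: SD 1.7, n = 12 per arm, two-sided 0.05, control change 0 with SD 0. A noncentral t distribution was used.

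- SE = 1.7/√12 = 0.491, with 11 degrees of freedom and critical value 2.201.
- Paired, difference 1.5: noncentrality 1.5/0.491 = 3.06, power 79.4% (stated 80%).
- Paired, difference 2: noncentrality 2/0.491 = 4.08, power 95.9% (stated 97%).
- Unequal-variance two-sample, 2 versus 0, SDs 1.7 and 0: the same SE and degrees of freedom, power 95.9% (stated 96%).

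All three agree within 2 points. All concern symptomatic UTI, and the plan states no error rate across outcomes.

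**2. Six outcomes, one test each.** If independent at 0.05: 1 − 0.95^6 = 1 − 0.735 = 26.5%. This counts a false rejection in either direction and between any arms.

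**3. The planned tests, simulated.** Three arms of 12, six normally distributed outcomes, no true effect on any, all tests at two-sided 0.05, 20,000 trials per row. The documents give no correlations, so a common correlation from 0 to 0.8 is assumed.

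| Correlation | Any significant ANOVA | False gentamicin benefit, gated pairwise tests | Same, or gentamicin-arm paired test | Any ANOVA or paired test, any arm |
|---|---|---|---|---|
| 0 | 26% | 11.7% | 21% | 63% |
| 0.3 | 25% | 11.2% | 19% | 60% |
| 0.5 | 22% | 9.8% | 16% | 53% |
| 0.8 | 15% | 6.6% | 11% | 39% |

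A repeat with 200,000 trials per row gave, at correlation 0.8, 14.4%, 6.3%, 10.8% and 39%. At correlation 0 it gave 26.3%, 11.8%, 20.7% and 63%. For a single outcome, the chance of a false gentamicin benefit is about 2% from the gated pairwise tests, and about 4% if the paired test also counts.

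**4. Cost of a plain adjustment.** Bonferroni over six gives 0.05/6 = 0.0083 per test, and 1 − (1 − 0.0083)^6 = 4.9% overall. On the plan's SDs (1.7 and 0), the critical value rises from 2.201 to 3.208 and power for symptomatic UTI falls from 96% to 78%.

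**5. Power if the named contrast is gentamicin versus saline.** Difference 2, 12 per arm, two-sided 0.05. The documents give no saline SD, so two values are assumed.

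- Saline SD 1.7: SE = √[(2.89 + 2.89)/12] = 0.694, noncentrality 2.88, 22 degrees of freedom, power 79%.
- Saline SD 0.85: SE = √[(2.89 + 0.7225)/12] = 0.549, noncentrality 3.65, 16.2 degrees of freedom, power 93%.

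**The case against.** The strongest reply is that symptomatic UTI is already the primary outcome in all but name. It comes first in the objective and in Hypothesis 1.1, and it is the sole basis of the power paragraph. In a study of 36 people labelled as feasibility, the gap is then largely one of labelling. This has force and limits the severity. But powering an outcome is not designating it, and the plan does not bind the report to it.

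Several stronger readings are tempting and do not hold:

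- **That a false benefit of gentamicin has a 26% chance.** The 26% includes errors in gentamicin's disfavour and differences between the two control groups. The between-group figure for a false benefit is about 6% to 12%.
- **That the paired tests make the 11% to 21% range, or the 39% to 63% range, the right measure.** Both hypotheses are comparisons with controls, so a within-arm change cannot by itself support them.
- **That the outcomes are independent.** Section 4 of the research procedures links a symptomatic UTI needing systemic treatment to antibiotic use, so at least two outcomes move together.
- **That Aim 1 implies a dozen or more tests.** Several Aim 1 items are findings such as stones or hydronephrosis, to which the planned t-tests and ANOVA do not clearly apply.
- **That the plan lets any one outcome establish success.** Hypothesis 1.1 joins its outcomes with a conjunction. If all had to succeed, error would not be inflated. The documents give no success rule either way.
- **That each test is stated to be at 0.05.** The level appears only in the power paragraph. It is a fair inference, since no other level is given and the ANOVA gate needs one.

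**Conclusion.** The point stands in a limited form. There are six hypothesised efficacy outcomes and no designated primary outcome, order or adjustment across them. Under no true effect, the chance of some significant ANOVA is 26% if the outcomes are independent and about 15% at correlation 0.8. For a false gentamicin benefit from the gated between-group tests it is about 6% to 12%, or roughly three to six times the 2% for one outcome. It reaches 11% to 21% only if a paired result in the gentamicin arm is also taken as evidence.

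These figures rest on an inferred 0.05 level, an assumed common correlation, normal data, exactly six outcomes, and a reader who treats one significant outcome as a positive result. The problem should be corrected, and it can be corrected in the text. It does not invalidate the design.

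**What to change.** In II.B.2:

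1. Designate symptomatic UTI as the single primary outcome, at two-sided 0.05, with one named between-group contrast tested directly.
2. If that is significant, test antibiotic courses and then multi-resistant organisms on the same contrast, each at 0.05, stopping at the first that is not significant. The error rate across these three tests stays at 5%.
3. Report urodynamic, blood pressure and all other outcomes, the remaining contrasts and the within-arm changes with 95% confidence intervals, labelled exploratory.
4. State the significance level in the analysis text as well as in the power paragraph.

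The choice of contrast has a price. Gentamicin versus saline is the only comparison in which participants are blinded (II.B.1), but the stated 96% is for gentamicin versus no instillation with a control SD of 0. If saline is chosen, restate power: about 79% with an assumed saline SD of 1.7, about 93% with 0.85, and lower if saline itself reduces UTIs.

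No participants or visits are added. The costs are fewer outcomes that can be claimed as confirmed and a less favourable stated power. Bonferroni over all six would also control error, but it lowers power for symptomatic UTI from 96% to 78% even on the plan's own SDs.

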1. Blinding Plan: This is a double-blind study whereby the investigators, research assistants, research nurse and participants will be blinded as to the drug treatment designation. Once participants have been assessed for eligibility and enrolled in the study, they will be randomized into 1 of 3 different groups. Participants randomized to either group I or II will be blinded to the intervention fantibiotic instillation in group I or placebo (saline alone) in group II]. Gentamicin sulfate will be prescribed for the research participants by the study physician or nurse practitioner and instilled under the direction of the research nurse. Thus, the participants in groups I and II will not be able to discern their assigned treatment. To ensure the double-blind, only the study physician or nurse practitioner as well as the pharmacy, all of whom are not associated with the data collection or data analysis, will be un-blinded. Note, the research nurse assisting participants with the instillation will be blinded. All participants will be identified by number and the instillation solutions (gentamicin or placebo) will be numbered with the pharmacy having access to the code specifying which instillations are active and which are placebo for each participant. The investigators and direct research team members will not be permitted to have knowledge of the group assignments. In the case of a drug related adverse event, the study physicians will evaluate the event and prescribe treatment that will minimize or completely resolve the event if minor or moderate in severity and it does not interfere with activities of daily living or quality of life (as determined by the participant). Should it be determined that the event has gotten worse, or if the participant can no longer tolerate the event, the study drug will be discontinued, and the participant will be terminated from study participation. There are no expected reasons to unmask the study treatment. The study physician or nurse practitioner will decide if the blind is to be broken or not. The blind will not "routinely" be broken when a serious adverse event (SAE) occurs. If an SAE is probably or definitely drug-related, the drug/placebo intervention will be stopped, and the participant treated appropriately. Emergency drug code envelopes will be created by the pharmacy at the study site. These will be labeled by participant randomization number and contain information, which will un-blind the treatment of the individual subject. These envelopes are to be used only in extreme emergencies, such as when an emergency situation exists in which the participant's treatment would be affected by knowledge of his drug therapy, and there is no time to contact the Medical Monitor. Note, that at the end of the study, participants will be un-blinded to the intervention designation by the study physician or nurse practitioner. If a participant was randomized to the no instillation group, however, he/she may re-enroll into the study and directly receive the gentamicin intervention and are not required to wait until the end of study, as all parties are un-blinded and aware of the treatment (standard of care) in this instance. All data from participants re-enrolling into the gentamicin-only group will be kept separate from those who are enrolled in the main study who are blinded.

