Urine collected for cultures will be collected as a clean-catch midstream technique from an immediately installed urine catheter or as a suprapubic aspiration from an installed catheter (52). For participants having a suprapubic catheter, the catheter will be clamped for 20 to 30 minutes until at least 5 mL of urine can be collected. The catheter will then be unclamped, and urine will be allowed to flow into a sterile plastic container. In those that use intermittent catheterization, participants will be required to first cleanse the urethral area with a castile soap towelette. A sterile 12 French straight catheter is inserted through the urethra into the bladder. The first portion of the urine stream should flow into the toilet in order to reduce the opportunities for contaminants to enter into the urine stream. The urine midstream is then collected into a clean container (any excess urine will be emptied into the toilet), Urine samples will be placed in

sterile storage vials and stored at 4C for less than 3 hours and sent to the Outpatient Care Center, Jewish Hospital for analysis. Symptomatic UTIs will be defined as a participant complaint of symptoms consistent with UTI (cloudy/foul smelling urine, fever, chills, increase in bladder and/or lower extremity spasms, worsening dysreflexia, leakage, or pain) combined with a positive leucocyte esterase and/or nitrates on dipstick urinalysis or a urine microscopy with > 10 WBC/HPF (white blood cells/high powered field) with a urine culture with >10⁵ bacteria/ml (46). Note that urine smell and cloudiness alone (i.e. without other symptoms) are not considered UTI signs, given their high prevalence in this catheterizing population. All cultured microorganisms will be identified to the species level and quantified as colony-forming units per ml (cfu/ml⁻¹) (16). If the microorganism(s) cultured is/are resistant to three or more different antimicrobial agents to which the microorganism would normally be susceptible, it will be defined as being multi-resistant. If a participant is diagnosed having a symptomatic UTI necessitating systemic antibiotics by the study physician/nurse practitioner, he/she will follow standard of care treatment under provider oversight. The study physician/nurse practitioner will recommend whether or not continuation of either the instillation or clamping protocol is appropriate for the participant during systemic antibiotic treatment.

5. Blood Draw

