
8. International SCI Data Sets

The International SCI Urinary Tract Infection data set (32) will be used to standardize the collection and reporting of information related to possible UTIs and includes such variables as: date of data collection, length of time of sign(s)/symptom(s), results of urine dipstick test for nitrite and leukocyte esterase, urine culture results and resistance pattern. This data set will be completed by the researcher(s). It will also be

used in combination with the International SCI Lower Urinary Tract Function Basic Data Set (Version 2), which contains information on the bladder-emptying method(s), urinary incontinence and any medications usage (59). The latter data set will be conducted by the researcher(s) with the participant.

D. Limitations

A limitation of this study will be the variable nature of the host urinary microbiome. Conventional thought has been that we all are colonized with similar organisms and thus, we should have similar responses to treatment interventions. However, through the Human Microbiome Project (60), we have learned that each of us have diverse microbial communities present in the gut, skin, and vagina (bladder was not investigated) and may help explain why some individuals benefit more from a particular treatment or are more susceptible to infections than others. Our approach in this study is to investigate the effects of a focused, placebo-controlled intervention in a specific population. In doing so, the results from this project may help differentiate responders from non-responders and can be integrated with current studies in the lab assessing the urinary proteome.

III. Human Subjects

There are approximately 1,275,000 Americans with a SCI. Fifty-six percent of the injuries occur in people aged 16 to 30, with an average age of 31, and 82% of the total population are male. Minorities make up 38% of SCI cases, and while every effort will be made to recruit minorities, based on the incidence rates, their participation may be limited. Every effort will be made to recruit women, though only about 18% of SCI patients are female.

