A medical event is defined within our program as any untoward or unfavorable medical occurrence in a human research participant that occurs during the enrollment period of a study. All medical events for study participants will be recorded in a log for tracking and reporting, as the team is made aware of them. Medical events that occur during a research visit will be reported to the study nurse and then elevated to the study physician if not immediately resolved. The physician will evaluate these medical events, to determine causality with relation to the research and referral for medical care. A weekly report of all medical events is generated by the research nurse and sent to the study physician (and physician assistant), the principal investigator, the regulatory core, and the study physical therapists for review of causality and follow-up. We have developed a table outlining the most common expected events in our SCI population. These events occur with this population on a daily basis. This table will allow the IRB and our staff to understand how expected and unrelated events will be documented and reported. If a physician outside the study team treats the medical event, the study physician will follow the event to assess the following:

- The medical condition affecting their medical eligibility for research
- Determination on causality of the event
- The event's effect on research assessments or training paradigms

All conclusions reached by the study physician will be reported to the PI. If another physician treats the medical issue the study physician will follow the individual to only assess whether the medical condition affects their medical eligibility in the study or any of the research assessments or training paradigms and will notify the principal investigator. These non-study related medical events are followed by the research team and will be reported to the IRB as outlined in Medical Reporting Table. A weekly report of all medical events is generated by the research nurse and sent to the study physician (and physician assistant), the principal investigator, and the study physical therapists. In this study, a medical event will only be reported if it occurs on the same day that the assessment associated with this study also occurs.

5. Data Safety and Monitoring Plan

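### The clinician role that the Blinding Plan unblinds also decides which UTIs need systemic antibiotics, so antibiotic courses started by study clinicians are exposed to unblinded judgement even for gentamicin versus saline

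*Combined protocol and SAP*

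**What the plan says.** The Blinding Plan (II.B.1) describes a double-blind trial in which participants in the gentamicin and saline groups do not know their assignment. It names the exceptions: "only the study physician or nurse practitioner as well as the pharmacy, all of whom are not associated with the data collection". The sentence goes on to exclude these people from data analysis too, and states that they will be unblinded. The study physician or nurse practitioner also prescribes the gentamicin.

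Item 4 of the research procedures (Urine Sample Collection and Culture) then says: "If a participant is diagnosed having a symptomatic UTI necessitating systemic antibiotics by the study physician/nurse practitioner", the participant receives standard care. The same role advises on whether instillation or clamping should go on during that treatment.

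Antibiotic use is an outcome. The Objectives ask whether instillation will "reduce the rate of symptomatic UTIs as well as the use of oral and intravenous antibiotics". Hypothesis 1.1 predicts "significantly decreased episodes of symptomatic UTIs, fewer courses of oral antibiotics" and fewer multi-drug resistant organisms than in controls.

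**The concern.** The stated reason for unblinding the physician or nurse practitioner is that they stand apart from the data. A clinician who decides to start an antibiotic course does not stand apart from an outcome that counts those courses, even if someone else fills in the form.

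The decision leaves room for judgement. Item 4 defines a symptomatic UTI but gives no rule for when one needs systemic treatment, and section I.D acknowledges a lack of consensus on which symptoms call for antibiotics. If a clinician's readiness to treat differed with knowledge of gentamicin or saline, the difference would look like a treatment effect on antibiotic use. The no-instillation arm is open in any case, so gentamicin versus saline is where blinding was meant to prevent this.

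**Working it through.** The plan gives no figure on this point. Its sample-size calculation (II.B.2) concerns symptomatic UTIs, not antibiotic courses, and nothing here changes it. The check is therefore a reading of the sections against each other.

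**Steps that lead to a recorded antibiotic course in the gentamicin and saline groups**

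1. *Complaint.* Item 4 begins its definition with the participant: "Symptomatic UTIs will be defined as a participant complaint of symptoms consistent with UTI". These participants are blinded.
2. *Tests.* The definition adds urinalysis and culture criteria. Nothing suggests that these depend on the assignment.
3. *Decision to treat.* Item 4 assigns this to the study physician/nurse practitioner. The Blinding Plan says that this role is unblinded.
4. *Recording.* Item 8 (International SCI Data Sets) has researchers complete the UTI data set. Researchers also conduct, with the participant, the data set that covers "urinary incontinence and any medications usage". The Blinding Plan keeps the direct research team blinded.

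Only step 3 is exposed.

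**Is step 3 moved to a blinded clinician anywhere?** The Blinding Plan, the research procedures and the Human Subjects section contain no such provision. The two places use the same pairing of roles, and nothing divides the duties between an unblinded prescriber and a blinded diagnosing clinician.

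**Are all courses affected?** No. Section III.E.4 foresees treatment elsewhere: "If a physician outside the study team treats the medical event", the study physician follows the event. Nothing shows that outside physicians know the assignment.

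**Is the role certainly unblinded?** The explicit statement says so. However, the Blinding Plan also has this role decide whether the blind is to be broken, and it provides sealed code envelopes for emergencies. Neither fits well with a clinician who already knows the assignment.

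**Extent**

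- Hypothesis 1.1 lists three outcomes: symptomatic UTI episodes, oral antibiotic courses and multi-drug resistant organisms. The decision in step 3 directly generates one of the three.
- Participants compared under the blind: 12 + 12 = 24 of 36.
- The documents do not say how many courses study clinicians would start, or how many of those decisions would turn on knowing the assignment. No bias estimate is possible.

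**The case against.** The strongest reply is that there is no literal contradiction. The Blinding Plan speaks of data collection and analysis, item 4 speaks of care, and item 8 leaves recording to researchers. That is right as far as it goes: the conflict is one of substance. It still stands, because the decision to treat is the outcome event that the researchers later record.

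Second, *physician or nurse practitioner* could mean that only one of the two is unblinded and the other treats. The plan elsewhere mentions several study clinicians, so staffing might allow this. But no section states such a split. If it is intended, writing it down resolves the point.

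Third, the text on breaking the blind suggests that the role may have been meant to be blinded. That weakens any claim about what happens in practice. It also shows that the Blinding Plan needs reconciling with itself.

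Fourth, this is called a feasibility study, antibiotic use does not appear in the list under Specific Aim 1, and the trial is powered on symptomatic UTIs. This limits the weight of the point. It does not remove it, since the Objectives say that efficacy will be tested and name antibiotic use.

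A reader might also infer that the symptomatic UTI count is decided by unblinded staff. The documents do not support that. The count needs a complaint from a participant who is blinded in these two groups, plus laboratory criteria, and researchers complete the data set. Who makes the final classification is not stated, so an unblinded classifier is possible but not shown.

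**Conclusion.** The point holds in a limited form and should be addressed. As written, the plan exposes antibiotic courses started by study clinicians to unblinded judgement, even for gentamicin versus saline. This conclusion assumes that the explicit statement of unblinding is taken at its word and that the paired roles mean the same people in both sections.

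The size and direction of any bias are unknown, and no percentage should be attached to it. A reader might try to scale the problem by assuming one course per UTI. Under that assumption every UTI is treated, so no discretion is left to bias, and the result would say nothing about size.

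Two other broad inferences also fail. Outside physicians' courses are not shown to be affected. The openness of the no-instillation arm is not a hidden flaw, because the Blinding Plan discloses it.

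**What to change.** Reconcile the Blinding Plan with item 4 so that whoever decides on systemic antibiotics is blinded between gentamicin and saline. The simplest way is for the pharmacy alone to hold the code while clinicians order numbered study instillation, with the existing emergency envelopes used for code breaks. This would also make sense of the sentence on who decides to break the blind.

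Add one data field that records, for each antibiotic course, whether a study clinician or an outside physician started it.

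The cost is protocol and pharmacy-procedure wording plus that field. Numbered solutions, a pharmacy-held code and envelopes are already planned, so no new staff are needed. The downside is that study clinicians would have to use the code-break procedure to learn an assignment.

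An alternative is to name an existing team member as a separate unblinded prescriber who takes no part in UTI diagnosis or antibiotic decisions. This works only if another, blinded clinician is available for those decisions.

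No criterion for treating a UTI is proposed.
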